## **8. RESEARCH QUESTION AND OBJECTIVES**

The aim of this study is to describe the baseline demographic and clinical characteristics, and HRU of adult ( $\geq 18$  years) COVID-19 patients who have been prescribed nirmatrelvir, ritonavir treatment in the outpatient setting.

Primary objective:

1. To describe the baseline demographic and clinical characteristics, including pre-existing comorbidities, of adult COVID-19 patients treated with and those not treated with nirmatrelvir, ritonavir.

Secondary objectives:

1. To evaluate the number and proportion of COVID-19 patients who meet the most up-to-date WHO recommendations for the use of therapeutics in the treatment of COVID-19 (ie, version 14, published 10Nov2023) in comparison to Kingdom of Bahrain national recommendations.
2. To assess adult COVID-19 patients' HRU and outcomes within the 28-day period

Exploratory objective:

1. To assess HRU and outcomes at day 5, 7 and 21 as exploratory analyses

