## **9. RESEARCH METHODS**

### **9.1. Study Design**

This will be a retrospective observational cohort study of patients diagnosed with COVID-19 in the Kingdom of Bahrain. Treated patients are defined as those have been prescribed nirmatrelvir, ritonavir and managed in the outpatient setting (eg, receiving medical treatment without being admitted to a hospital for COVID-19) while control group is those not treated with nirmatrelvir, ritonavir. Data will be from the *I-Seha electronic medical records* and descriptive analyses will be conducted for these two cohorts and will compare healthcare resource use in patients treated with nirmatrelvir, ritonavir and those not treated with nirmatrelvir, ritonavir.

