**Table 1. Cohort Definitions**

Name	Criteria	Identification Period	Index Date	Follow Up Period
Treated patients	Patients diagnosed with COVID-19 and treated with Paxlovid™	After Paxlovid™ availability during the same dominant variant (ie, Omicron or Delta etc.) era timeframe as Cohort	Paxlovid™ prescription written date or dispense date*  If neither of the above are available, the COVID-19 diagnosis date may be used as the index date	28 -days follow up
Control group	Patients diagnosed with COVID-19 and not treated with Paxlovid™	After Paxlovid™ availability during the same dominant variant (ie, Omicron or Delta etc.) era timeframe as Cohort	Date of COVID-19 diagnosis	28 -days follow up

\*If both dates are available in the data source, the most recent date should be used as the index date for Cohort.

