### 9.2.2. Exclusion Criteria

**There are no exclusion criteria for this study.**

## 9.3 Variables

The following variables are used to obtain comprehensive descriptive results.

1. Demographics
2. Date of symptoms
3. Viral variant analysis where available (type of viral variant ie, omicron, delta etc.)
4. PCR date along with CT Value

5. Co-morbidities and
6. BMI if  $\geq 30$
7. Symptoms at presentation
8. COVID 19 vaccine status (NB 92% of population has been vaccinated -with at least one dose of COVID 19 vaccine- in Bahrain)
9. Hospital admission
10. Follow up looking at compliance and reason of non-compliance
11. Day 5,7, 21 and 28 symptoms for COVID-19 patients who receive and HRU limited to admission (ICU, ward, need for oxygen therapy) or death
12. Date of symptoms resolution if applicable

**Table 2** Table 2 below depicts the patient demographics that will be accessed during the baseline and follow-up periods. The baseline period is defined as one year before the index date. Comorbidities (full list in [Table 6](#)) and maintenance medication usage for chronic conditions (eg, statins, antihypertensives, etc.) will be described during the baseline period and follow-up periods and are listed in [Table 3](#).

Risk factors for severe COVID-19, intensive care unit (ICU) usage, invasive mechanical ventilation (IMV) usage, supplemental oxygen use, non-invasive ventilation, and high-flow nasal cannula usage are depicted in [Table 5](#) and will be extracted from the *I-Seha* national electronic health record database.

Where applicable, emerging treatment patterns may be assessed as the time from symptom onset to COVID-19 diagnosis, time from symptom onset to treatment initiation, and the time from COVID-19 diagnosis to treatment initiation as illustrated in [Table 5](#).

10Nov23 WHO recommendations for Paxlovid treatments to define: 1. COVID-19 patients who meet the WHO criteria for “strongly recommended” 2. COVID-19 patients who meet the WHO criteria for “conditionally recommended”, and 3. COVID patients who are not falling into categories 1 or 2 will be used.

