## 9.7. Data Analysis

Detailed methodology for summary and statistical analyses of data collected in this study will be documented in a statistical analysis plan (SAP), which will be dated, filed, and maintained by the sponsor. The SAP may modify the plans outlined in the protocol; any major modifications of primary endpoint definitions or their analyses would be reflected in a protocol amendment.

A separate statistical analysis plan will provide analysis and programming details along with detailed table shells. A sample of the table of results expected from the primary aim of this descriptive study is listed in [Table 8](#).

All descriptive statistics will be presented as n, % for the categorical variables, or mean  $\pm$  SD, median (interquartile range) for the numerical (continuous variables), as appropriate.

Study sample will be stratified by age group: 18-29, 30-49, 50-64, 65-74,  $\geq$ 75. Numerical outcomes included the number of COVID-19 vaccines received, date of last vaccination, days from last COVID-19 vaccination to date of Paxlovid™ treatment (eg, Prescription and dispensing date), days from COVID-19 diagnosis to date of Paxlovid™ treatment (eg, dispensing date), days from COVID-19 symptom onset to date of Paxlovid™ treatment (eg, dispensing date).

Categorical outcomes included comorbid conditions and COVID-19 therapy. Possible comorbid conditions include obesity (BMI  $\geq$  30), chronic kidney disease, diabetes mellitus, primary and Secondary Immunosuppressive disease or immunosuppressive treatment, cardiovascular disease (including congenital heart disease) or hypertension, active immunosuppressive disease (such as lymphoma, leukemia, etc.), active Immunosuppressive treatment (Chemo, Steroids, etc.) (Immunocompromised, defined in [ANNEX 2](#). **IMMUNOCOMPROMISED ICD-10 CODE LIST**).

WHO guidelines on COVID-19 therapeutics include the following groups

- **High risk:** people who are immunosuppressed; estimated hospitalization rate of 6%.
- **Moderate risk:** >65 years of age, conditions like obesity, diabetes and/or chronic conditions including chronic obstructive pulmonary disease, kidney or liver disease, cancer, with disabilities, and with comorbidities of chronic disease; estimated hospitalization rate of 3%.

- **Low risk:** those who are not in the high or moderate risk categories; low risk of hospitalization (0.5%) – most people are low risk.

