### **Data source**

This study will involve a secondary data analysis of COVID-19 patients' data from the ISeha Electronic health records. The following data will be used: patient demographic characteristics, clinical characteristics, and COVID-19 disease outcomes. The ISeha EHR data will be anonymized. Demographic and clinical data from eligible patients were recorded in ISeha electronic health records by medics on the ward. Patient-reported symptom outcomes in the five-days following Paxlovid prescription were determined by a follow-up telephone call.

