## 1.2 STUDY OBJECTIVES

The overall aim of this study is to examine the baseline demographic, clinical, and outcome characteristics of COVID-19 patients who received Paxlovid.

PFIZER CONFIDENTIAL

CT24-WI-GL03-RF03 2.0 *Non-Interventional Statistical Analysis Plan For Secondary Data Collection*  
*Study 01-Jun-2020*  
Page 6 of 22

The objectives are

- (i) to describe the demographic, clinical, and outcome characteristics of COVID-19 patients who received Paxlovid and COVID-19 patients who were offered, but refused Paxlovid
- (ii) to examine differences in the demographic characteristics (e.g., age, sex, nationality, type of outpatient encounter, vaccination status) between COVID-19 patients who received Paxlovid and COVID-19 patients who refused Paxlovid,
- (iii) to examine differences in the clinical characteristics (e.g., comorbidities, symptoms, duration of symptoms) between COVID-19 patients who received Paxlovid and COVID-19 patients who refused Paxlovid over a five-day follow-up,
- (iv) to examine differences in outcomes (e.g., hospitalisations, time spent in an intensive care unit, time spent with invasive mechanical ventilation, supplemental oxygen usage, re-admission to hospital, deaths) between COVID-19 patients who received Paxlovid and COVID-19 patients who refused Paxlovid over a five-day follow-up.
- (v) To examine differences in the proportion of COVID-19 patients who meet the most up-to-date WHO recommendations for the use of therapeutics in the treatment of COVID-19 (ie, version 14, published 10Nov2023) in comparison to Kingdom of Bahrain national recommendations.

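### SAP objective (iv) compares hospital outcomes and deaths over five days, where the protocol sets 28 days and makes day 5 exploratory, with no flag or reason

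*SAP*

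**What the plan says.** **Protocol.** Secondary objective 2 in section 8 is to assess "HRU and outcomes within the 28-day period". The exploratory objective in the same section is "To assess HRU and outcomes at day 5, 7 and 21 as exploratory analyses". Table 1 gives treated patients and controls the same follow-up, "28 -days follow up". Section 9.1 states that the analyses "will compare healthcare resource use in patients treated with nirmatrelvir, ritonavir and those not treated with nirmatrelvir, ritonavir". Item 11 of section 9.3 lists "Day 5,7, 21 and 28 symptoms for COVID-19 patients who receive and HRU limited to admission (ICU, ward, need for oxygen therapy) or death". Section 9.7 allows departures: "The SAP may modify the plans outlined in the protocol". It requires a protocol amendment only for major changes to the primary endpoint or its analysis.

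**SAP.** Objective (iv) in section 1.2 covers hospitalisation, ICU time, invasive ventilation time, oxygen use, readmission and death. It sets the comparison as "re-admission to hospital, deaths) between COVID-19 patients who received Paxlovid and COVID-19 patients who refused Paxlovid over a five-day follow-up". Objective (iii), on clinical characteristics, carries the same five-day limit. The only other five-day statement is under Data source: "Patient-reported symptom outcomes in the five-days following Paxlovid prescription were determined by a follow-up telephone call". Tables 2 and 4 define outcomes over a follow-up period whose length is never given. Sections 1.12 and 1.13 plan tests, confidence intervals and effect sizes for disease outcomes and state no window. The Table 7 shell has no window either.

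**The concern.** Five days is the only follow-up length in the SAP, and it is attached to the comparison of the main resource-use outcomes and deaths. That puts the inferential comparison at a time point the protocol calls exploratory. The protocol's own 28-day window is left without a specified between-group comparison.

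Admissions, ICU use, readmissions and deaths from day 6 to day 28 would fall outside the comparison. Some outcomes are also constrained by the window itself. ICU or ventilation time counted within it cannot exceed five days per patient, and a readmission requires admission, discharge and a second admission inside five days. An analyst who notices the conflict would have to choose the window during the analysis, possibly after seeing results.

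**Working it through.** There is no planned figure to reproduce: the study is descriptive and states no power or event target for this comparison. The check is a comparison of text, plus two short calculations.

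**1. The two documents side by side**

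| Item | Protocol | SAP |
|---|---|---|
| Window for resource use and outcomes | 28 days (section 8, secondary objective 2) | 5 days for the comparison (section 1.2, objective iv) |
| Cohort follow-up | 28 days, both cohorts (Table 1) | Follow-up period used, length not defined (Tables 2 and 4) |
| Status of day 5 | Exploratory, with days 7 and 21 (section 8) | The only follow-up length stated |
| Between-group comparison of resource use | Planned (section 9.1) | Planned (objective iv, sections 1.12 and 1.13) |
| Acknowledgement of the change | Not applicable | None |

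**2. Share of follow-up compared**

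- Covered: 5 / 28 = 0.179, or 18% of the days.
- Left out: (28 − 5) / 28 = 23 / 28 = 0.821, or 82% of the days.
- The SAP Table 4 definitions also exclude the first 24 hours after Paxlovid initiation. That is 1/5 = 20% of a five-day window, against 1/28 = 3.6% of the protocol's window.

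**3. Could elapsed time explain five days?**

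- Last identification date: 30 November 2022 (Protocol 9.5).
- Close of a 28-day window from that date: 30 November + 28 days = 28 December 2022.
- Start of data collection: 15 January 2024 (Protocol section 6).
- Gap: 365 days to 28 December 2023, plus 18 days to 15 January 2024 = 383 days.

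Every patient's 28 days had passed long before extraction. If a treated patient's index date fell a few days after diagnosis, the gap would shrink by only those few days.

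**4. Could the data source explain it?**

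The five-day telephone call collects symptoms reported after a Paxlovid prescription. It could bear on objective (iii). It does not explain a limit on admissions and deaths: Protocol 9.4.1 has these extracted from the health record for untreated patients, and Protocol 9.4 describes the database as complete for utilisation submitted for payment.

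**The case against.** The strongest reply is that the five-day wording appears only in the objectives and the telephone-call sentence. The outcome definitions, the methods sections and the Table 7 shell carry no window, and the only follow-up period defined in either document is 28 days. On this reading the SAP is ambiguous, perhaps through a drafting carry-over from the call, and a programmer might produce 28-day results anyway. This does not remove the problem. Text without a window cannot override the explicit limit in objective (iv), and a reader who looks in the SAP for a follow-up length finds only five days.

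Several other points stand, and they limit the claim:

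- Protocol 9.7 lets the SAP modify the plan, and these outcomes are secondary. No amendment rule is broken; the fault is a conflict that is neither acknowledged nor explained.
- SAP objective (i) describes outcomes with no window, so a 28-day description is not excluded. What is missing is the 28-day comparison.
- No single protocol sentence states that comparison. It follows from section 9.1 read with Table 1 and secondary objective 2. Item 11 of section 9.3 is a broken sentence and supports the reading only in part.
- The study is descriptive and the SAP calls the work exploratory. It nevertheless plans p-values and confidence intervals on these outcomes, and those need a window.
- Day-28 data may be incomplete, since the SAP extracts variables only where available. The fix allows for this.

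**Conclusion.** The concern holds. As written, the SAP's comparison of hospital outcomes and deaths covers 18% of the protocol's follow-up days and omits 82%, at a time point the protocol treats as exploratory, with no reason given. This must be fixed before analysis because the window determines every follow-up count in the outcome comparison.

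The conclusion rests on the text and on the dates in step 3, with no modelling assumption. The share of events lost, and any loss of power, cannot be derived because the documents give no event timing. The primary objective, on baseline characteristics, is not affected.

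**What to change.** In the SAP:

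1. In objective (iv), replace the five-day limit with 28 days from the index date in Protocol Table 1, and state that index date for each cohort. The protocol's dates differ: prescription or dispensing for treated patients (diagnosis if neither is available), and diagnosis for controls. The only index date the SAP names is the positive test, for concomitant medicines.
2. Define the follow-up period in Tables 2, 4 and 7 as those 28 days. The death rows in the Table 6 shell then take the same definition, because Table 2 defines death by the follow-up period.
3. List days 5, 7 and 21 as exploratory.
4. In the Table 7 shell, report follow-up outcomes separately from use in the baseline year. Many of the Table 4 definitions name both periods, but the shell has one row per outcome, so a 28-day result could not be read from it.
5. If the extracted data do not reach day 28, declare the shorter window and justify it.

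The cost is a few sentences and some table-shell edits. The protocol already sets 28 days and needs no change for this. The one task beyond drafting is to confirm that day-28 record data are available for both cohorts.

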## **HYPOTHESES AND DECISION RULES**

*Not applicable*

### **1.3 STATISTICAL HYPOTHESES**

*Not applicable*

### **1.4 STATISTICAL DECISION RULES**

*Not applicable*

## **ANALYSIS SETS/POPULATIONS**

### **1.5 FULL ANALYSIS SET**

The full analysis set will consist of approximately 8263 adult COVID-19 patients with pre-existing comorbidities who attended outpatient clinics in the Kingdom of Bahrain. It includes approximately 3000 patients who received Paxlovid and approximately 1000 COVID-19 patients who were offered Paxlovid therapy but who refused treatment.

### **1.6 SAFETY ANALYSIS SET**

Not applicable

PFIZER CONFIDENTIAL

CT24-WI-GL03-RF03 2.0 *Non-Interventional Statistical Analysis Plan For Secondary Data Collection*  
Study 01-Jun-2020  
Page 7 of 22

## 1.7 OTHER ANALYSIS SET

Not applicable

## 1.8 SUBGROUPS

Not applicable

## ENDPOINTS AND COVARIATES

Patients were treated according to clinical practice. Therefore, the decision of what measures to record was not pre-specified in the protocol. Variables from EHRs that align with the data required by the protocol will be used.

The following variables will be extracted from EHRs, if available:

**Table 1: Patient Demographic Variables**

Variable	Operational definition
Group	Received Paxlovid or did not receive Paxlovid
Age	Age will be defined as of the date of COVID-19 diagnosis using a PCR test and will be used to assign patients to age groups: 18-29, 30-49, 50-64, 65-74, $\geq 75$ years and unknown/missing age
Sex	Female, male and unknown/missing sex patients
Nationality	Nationality of the patient (Bahrain, other Middle East and North Africa, India, Pakistan, South East Asia, Caucasian)
Enrollment Date Place of Service (POS)	Type of outpatient encounter during the enrollment date (e.g., office visit, emergency room (ER), outpatient hospital, other, etc.)
Enrollment Date	Date (defined as MM/YYYY) of the enrollment date specified
Specialty of Provider at enrollment Date	Provider specialties present during the enrollment date. Patients with no provider specialty recorded will be included in an “Unknown/missing specialty” category
COVID-19 Symptom Onset Date	Date of symptom onset prior to presentation to healthcare facility

PFIZER CONFIDENTIAL

CT24-WI-GL03-RF03 2.0 *Non-Interventional Statistical Analysis Plan For Secondary Data Collection*  
*Study 01-Jun-2020*  
 Page 8 of 22

Time to COVID-19 Symptom Resolution	Time from onset of COVID-19 symptoms to resolution of symptoms
Date of COVID-19 Vaccination	Date of each COVID-19 vaccination received. Note: patient-specific vaccination history may require more than 6-months pre-index time period.
Date of Paxlovid prescription written and/or fill history (e.g., prescription claim)	Date of Paxlovid prescription written or fill history. Note: if both dates are available within the database, use the most recent date provided.

**Table 2: Clinical Characteristic Variables**

Variable	Operational definition
Comorbidities	Asthma, emphysema, chronic obstructive pulmonary disease (COPD), hypertension, diabetes, obesity, cerebrovascular disease, neurological disease, chronic kidney disease, chronic liver disease, malignancy, etc.
Risk Factors for Severe COVID-19	
 
• Age <math>\geq 50</math> years
 
• Obesity (BMI <math>\geq 35</math>)
 
• Chronic kidney disease (eGFR <math>\geq 30</math> ml/min)
 
• Diabetes Mellitus
 
• Primary and Secondary Immunosuppressive disease or immunosuppressive treatment
 
• Cardiovascular disease (including congenital heart disease) or hypertension
 
• Chronic lung diseases (for example, chronic obstructive pulmonary disease, asthma [moderate-to-severe], interstitial lung disease, cystic fibrosis, and pulmonary hypertension)
 
• Sickle cell disease
 
• Neurodevelopmental disorders (for example, cerebral palsy) or other conditions that confer medical complexity (for example, genetic or metabolic syndromes and severe congenital anomalies)
 
• Having a medical-related technological dependence (for example, tracheostomy, gastrostomy, or positive pressure ventilation [not related to COVID-19])
 

PFIZER CONFIDENTIAL

CT24-WI-GL03-RF03 2.0 *Non-Interventional Statistical Analysis Plan For Secondary Data Collection*  
 Study 01-Jun-2020  
 Page 9 of 22

Patient-reported COVID-19 symptoms	List of COVID-19 symptoms to be added by study team (US, CDC definition). 
 
1- Stuffy or runny nose
 
2- Sore throat
 
3- Shortness of Breath
 
4- Cough
 
5- Low energy/Tiredness/fatigue
 
6- Muscle ache/body aches
 
7- Headache
 
8- Chills or shivering
 
9- Feeling hot/feverish
 
10- Nausea or vomiting
 
11- Diarrhea
 
12- Loss of sense of smell
 
13- Loss of sense of taste
 

Death	Died on or after the enrollment date in the follow up period
Inpatient Death	Died during a hospitalization in the follow-up period

**Table 4: COVID-19 disease outcome variables**

Variable	Operational definition
Hospitalizations	Number of all-cause and COVID-related hospitalizations (excluding within 24 hours of Paxlovid initiation) during the baseline and follow-up period per patient
Number of Hospitalizations per Patient	The number of hospitalizations per patient in the baseline and follow-up periods for all-cause and COVID-related hospitalizations (excluding within 24 hours of Paxlovid initiation)
Number of Hospitalizations per Patient among Patients with Readmissions	The number of all-cause and COVID-related hospitalizations (excluding within 24 hours of Paxlovid initiation) per patient in the baseline and follow-up periods will be described among patients with readmissions during the same period. The cause for readmission will be reported when available.
Time to First Outpatient Encounter	Time from COVID-19 diagnosis to the earliest outpatient encounter to occur after diagnosis during the baseline period.

PFIZER CONFIDENTIAL

Hospital Length of Stay	The total length of stay (LOS) recorded for all hospitalizations during the baseline period and follow-up period in days (excluding within 24 hours of Paxlovid initiation)
ICU/Non-ICU LOS	The total number of days in the intensive care unit (ICU) and the number of days that were not spent in the ICU (non-ICU) recorded for all hospitalizations during the baseline period and follow-up period in days (excluding within 24 hours of Paxlovid initiation)
IMV/No IMV LOS	The total number of days with and without invasive mechanical ventilation (IMV) recorded for all hospitalizations during the baseline period and follow-up period in days (excluding within 24 hours of Paxlovid initiation)
ICU Admission	ICU admission during COVID-related hospitalizations in the baseline and follow-up periods (excluding within 24 hours of Paxlovid initiation)
IMV Usage	IMV (i.e., intubation and mechanical ventilation) usage, including extracorporeal membrane oxygenation (ECMO), during COVID-related hospitalizations in the baseline and follow-up periods (excluding within 24 hours of Paxlovid initiation)
Supplemental Oxygen Usage	supplemental oxygen usage during COVID-related hospitalizations in the baseline and follow-up periods (excluding within 24 hours of Paxlovid initiation)
Non-invasive Ventilation Usage	Non-invasive ventilation usage during COVID-related hospitalizations in the baseline and follow-up periods (excluding within 24 hours of Paxlovid initiation)
High-flow Nasal Cannula Usage	High-flow nasal cannula usage during COVID-related hospitalizations in the baseline and follow-up periods (excluding within 24 hours of Paxlovid initiation)
Hospital Discharge Status	Patient discharge status for COVID-related hospitalizations during the baseline and follow-up periods (excluding within 24 hours of Paxlovid initiation)

PFIZER CONFIDENTIAL

CT24-WI-GL03-RF03 2.0 *Non-Interventional Statistical Analysis Plan For Secondary Data Collection*  
*Study 01-Jun-2020*  
 Page 11 of 22

Time from COVID-19 Test to Paxlovid Treatment	Time from the earliest COVID-19 test in the baseline period to the earliest date of Paxlovid prescription written date AND dispense date.
COVID-19 Lab Tests with Positive Result	COVID-19 lab test with a positive result during the baseline and follow-up periods.
COVID-19 Lab Test with Variant Type	When available, COVID-19 variant of concern (VOC) during the baseline period.
Treatment drugs being receiving at the index date	-Use Positive test as the INDEX Date and record use of any medicine listed in the potential DDI/Contraindications section of the EUA/:Label
Monoclonal Antibody Usage	Monoclonal antibody usage during the baseline and follow-up periods. Monoclonal antibody usage will include tocilizumab and bamlanivimab/etesevimab. (Yes/No)
Antiviral Usage	Antiviral therapy usage during the baseline and follow-up periods. Antiviral therapy usage will include remdesivir, nirmatrelvir/ritonavir (paxlovid) and molnupravir. (Yes/No)
Steroid therapy	Steroid therapy during admission (Yes/No)

PFIZER CONFIDENTIAL

CT24-WI-GL03-RF03 2.0 *Non-Interventional Statistical Analysis Plan For Secondary Data Collection*  
*Study 01-Jun-2020*  
 Page 12 of 22

WHO guidelines on COVID-19 therapeutics include the following groups

- **High risk:** people who are immunosuppressed; estimated hospitalization rate of 6%.
- **Moderate risk:** >65 years of age, conditions like obesity, diabetes and/or chronic conditions including chronic obstructive pulmonary disease, kidney or liver disease, cancer, with disabilities, and with comorbidities of chronic disease; estimated hospitalization rate of 3%.
- **Low risk:** those who are not in the high or moderate risk categories; low risk of hospitalization (0.5%) – most people are low risk.

Using these criteria, we will look at frequency and percentage of COVID-19 patients who will fall in those criteria to understand strongly recommended or conditionally recommended use of Paxlovid™ in comparison to the country of issue recommendations.

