**Table 4. HRU Data**

Variable	Operational definition
Hospital Length of Stay	The total length of stay (LOS) recorded for all hospitalizations during the baseline period and follow-up period in days (excluding within 24 hours of Paxlovid™ initiation).
ICU/Non-ICU LOS	The total number of days in the intensive care unit (ICU) and the number of days that were not spent in the ICU (non-ICU) recorded for all hospitalizations during the baseline period and follow-up period in days (excluding within 24 hours of Paxlovid™ initiation).
IMV/No IMV LOS	The total number of days with and without invasive mechanical ventilation (IMV) recorded for all hospitalizations during the baseline period and follow-up period in days (excluding within 24 hours of Paxlovid™ initiation).
Hospitalizations (Count and Percentage)	The count and percentage of patients with all-cause and COVID-related hospitalizations (excluding within 24 hours of Paxlovid™ initiation) during the baseline and follow-up period.
Number of Hospitalizations per Patient	The number of hospitalizations per patient in the baseline and follow-up periods for all-cause and COVID-related hospitalizations (excluding within 24 hours of Paxlovid™ initiation) will be described.
Number of Hospitalizations per Patient among Patients with Readmissions	The number of all-cause and COVID-related hospitalizations (excluding within 24 hours of Paxlovid™ initiation) per patient in the baseline and follow-up periods will be described among patients with readmissions during the same period. The cause for readmission will be reported when available.
Time to First Outpatient Encounter	Time from COVID-19 diagnosis to the earliest outpatient encounter to occur after diagnosis during the baseline period.

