**Table 7: Descriptive statistics for outcome variables**

Outcome Variables	Group		P-value	Effect size
	Paxlovid	Control		
Hospitalizations, % (n)				
Number of hospitalizations per patient, mean (SD)				
Number of hospitalizations per patient among patients with readmissions, % (n)				
Time to first outpatient encounter, mean (SD)				
ICU Admission, % (n)				
Hospital Length of Stay, mean (SD)				
ICU/Non-ICU LOS, mean (SD)				
IMV/No IMV LOS, mean (SD)				
Treatment				
IMV Usage, % (n)				
Supplemental Oxygen Usage, % (n)				
Non-invasive Ventilation Usage, % (n)				
High-flow Nasal Cannula Usage, % (n)				
Hospital Discharge Status				
Went home, % (n)				
Transfer to skilled nursing facility, % (n)				

PFIZER CONFIDENTIAL

CT24-WI-GL03-RF03 2.0 *Non-Interventional Statistical Analysis Plan For Secondary Data Collection Study* 01-Jun-2020

Page 20 of 22

Transfer to other healthcare facility, % (n)				
Transfer to other long-term care facility, % (n)				
Transfer to hospice, % (n)				
Death, % (n)				
Medication Usage, % (n)				
Antibiotic, % (n)				
Antiviral (incl. Paxlovid, COVID-19 monoclonal antibodies), % (n)				
Antithrombotic, % (n)				
Anti-inflammatory (incl. steroids), % (n)				

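### Hospital-use outcomes are defined over the year before index plus follow-up and shown in one row each, so no planned output gives the 28-day resource-use objective

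*SAP*

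**What the plan says.** Secondary objective 2 (protocol section 8) is "To assess adult COVID-19 patients' HRU and outcomes within the 28-day period". Protocol Table 1 gives both cohorts "28 -days follow up". Protocol section 9.3 states: "The baseline period is defined as one year before the index date". The SAP does not redefine baseline.

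The operational definitions use a different window from the objective. SAP Table 4 defines hospitalizations as "Number of all-cause and COVID-related hospitalizations (excluding within 24 hours of Paxlovid initiation) during the baseline and follow-up period per patient". Protocol Table 4 defines hospital stay as "The total length of stay (LOS) recorded for all hospitalizations during the baseline period and follow-up period in days". The same two-period wording is attached to admissions per patient, readmissions, ICU and ventilation days, ICU admission, invasive ventilation, oxygen, non-invasive ventilation, high-flow cannula and discharge status (protocol Tables 4 and 5; SAP Table 4). Death and inpatient death, by contrast, are confined to follow-up (protocol Table 3; SAP Table 2).

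The shell for SAP Table 7, the outcome table, has one row per measure (discharge status is broken down by category), with columns for Paxlovid, control, p-value and effect size. It has no period split and no day-28 row, and the SAP's analysis sections add no period-specific analysis. SAP objective (iv) sets the outcome comparison with "COVID-19 patients who refused Paxlovid over a five-day follow-up". A 28-day window appears nowhere in the SAP.

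**The concern.** An admission before index cannot result from taking or refusing the drug. If such admissions enter the outcome rows, two things can happen. Where prior-year use is similar in the two groups, it dilutes a real follow-up difference towards none. Where prior-year use differs between acceptors and refusers, a baseline characteristic appears as an outcome difference with a p-value beside it.

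Even for pure description, a rate that includes the preceding year is not the 28-day rate the protocol asks for. Mortality and hospitalization would also sit in the same report on different time windows.

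**Working it through.** The plan gives no figure on this point, so there is none to reproduce. The steps below size the literal reading.

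**1. Share of the window before index.** Inputs: baseline of 365 days (protocol 9.3); follow-up of 28 days (protocol Table 1) or 5 days (SAP objective iv).
- 365 / (365 + 28) = 365/393 = 92.9%. Counting the index day separately gives 365/394 = 92.6%.
- 365 / (365 + 5) = 365/370 = 98.6%.

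These are shares of calendar time, not of events. For controls, index is the diagnosis date, so the time lies before diagnosis.

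**2. Which rows are exposed.**

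| Rows | Stays counted | Pre-index contribution |
|---|---|---|
| Hospitalizations, admissions per patient, readmissions | All-cause and COVID-related | Any admission in the prior year (all-cause part) |
| Hospital, ICU/non-ICU and IMV/no-IMV days | All hospitalizations | Any hospital day in the prior year |
| ICU admission, IMV use, oxygen, NIV, high-flow cannula, discharge status | COVID-related only | Earlier COVID admissions, or care before index in the same episode |
| Death, inpatient death | Follow-up only | None |

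**3. Dilution, as an illustration.** Let r be the 28-day risk and b the prior-year risk of any admission, assumed independent. Pooled risk = 1 − (1 − b)(1 − r). Control r = 3%, the moderate-risk hospitalization rate quoted in both documents. Treated r = 3% × (1 − 0.88) = 0.36%, from the quoted 88% reduction; that figure is for hospitalization or death, so applying it to hospitalization alone is an assumption. The true risk ratio is 0.12. The values of b are assumed and equal in the two groups.

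| b | Treated | Control | Pooled risk ratio |
|---|---|---|---|
| 5% | 1 − 0.95 × 0.9964 = 5.34% | 1 − 0.95 × 0.97 = 7.85% | 0.68 |
| 10% | 1 − 0.90 × 0.9964 = 10.3% | 1 − 0.90 × 0.97 = 12.7% | 0.81 |
| 20% | 1 − 0.80 × 0.9964 = 20.3% | 1 − 0.80 × 0.97 = 22.4% | 0.91 |

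**4. Power under a smaller effect.** Assume 28-day risks of 1.5% and 3%, with the SAP's approximate 3000 treated and 1000 controls and two-sided alpha 0.05 (the SAP does not state sidedness). On follow-up only, the risk ratio is 0.50 and power about 82%. With b = 2%, 5%, 10% or 20% pooled in, the risk ratio is 0.70, 0.82, 0.89 or 0.95, and power about 55%, 35%, 21% or 12%.

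**5. Spurious difference, as an illustration.** Assume no drug effect (r = 3% in both groups) and prior-year risks of 10% treated and 15% refusers. The pooled risks are 1 − 0.90 × 0.97 = 12.7% and 1 − 0.85 × 0.97 = 17.55%, a ratio of 0.72. With assumed prior-year risks of 8% and 12% at the same group sizes, the pooled row would be significant about 90% of the time. Both cases require that the imbalance survives matching.

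**6. A related definition.** Time to first outpatient encounter is measured from diagnosis to an encounter after diagnosis, yet within the baseline period. For controls, index is diagnosis, so no baseline day follows diagnosis. For treated patients, only the gap between diagnosis and prescription or dispensing would qualify.

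**The case against.** The strongest reply is that neither document says the two periods are added together. The wording can be read as reporting each period separately, and the readmission definition, which refers to patients readmitted within the same period, leans that way. The Table 7 shell is visibly abbreviated: it puts ICU and non-ICU days in one row and does not separate all-cause from COVID-related admissions, so a missing split is weak evidence of summing. The intent looks post-index too: protocol section 9.3 lists days 5, 7, 21 and 28, and SAP objective (iv) is about follow-up. A reader might infer that the plan deliberately chose a 393-day outcome; the documents do not support that.

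This stands as to intent. It does not rescue the text. Separate reporting is stated nowhere, the shell has no place for it, and the stay definition asks for a total over both periods. If separate reporting is meant, it still has to be written.

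Three further limits also stand. A reader might take 93% as the share of events; it is not, and the documents give no prior-year rates from which to derive that share. A reader might treat every row as equally affected, but six measures are restricted to COVID-related stays. And the SAP plans propensity-score matching on care-seeking in the prior 365 days, including visit counts, subject to data availability. If that balances prior-year use, the spurious-difference scenario falls away and dilution remains.

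The study is descriptive and its tests exploratory, but the SAP does plan p-values and effect sizes for these outcomes, and a 28-day description would be wrong regardless of testing.

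**Conclusion.** The point holds on the literal text. The outcome definitions include the year before index, the results shell does not separate the periods, and secondary objective 2 has no planned output. The exposed window is 365 of 393 days, or 365 of 370 under the SAP's five days. The effect is largest for all-cause hospitalization and the length-of-stay rows, and smaller for the COVID-related rows.

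The risk ratios and power figures are illustrations that rest on assumed prior-year rates, independence of the two periods and, for the trial-based effect, a reduction quoted for a composite endpoint. They show that the distortion could be material; they do not estimate it. It would go too far to say that most counted events precede index, or that a false difference will appear: the first needs event rates the documents lack, and the second requires that matching fails to balance prior-year use.

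**What to change.** - In SAP Table 4 and protocol Tables 4 and 5, define every hospitalization, stay, ICU, ventilation, oxygen and discharge outcome on the 28 days after index only, with days 5, 7 and 21 as exploratory time points.
- Compute SAP Table 7 on follow-up events only and label it with the window.
- Report prior-year utilization as a separate baseline row in SAP Table 3.
- Reconcile the five-day follow-up in SAP objective (iv) with the protocol's 28 days. Without this, the corrected SAP Table 4 would contradict the SAP's own objective.
- Restate time to first outpatient encounter so that its window can contain the event it measures.

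The cost is SAP wording, a protocol clarification, one extra baseline row and a relabelled shell. No new kind of data should be needed: the current definitions already require each stay to be placed before or after index. The abstraction form should capture admission and discharge dates so that this can be done.
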